### 5.4.3 Other Efficacy Analysis/es

In this section the statistical analyses for the defined other efficacy endpoints will be described. For all endpoints, descriptive statistics and inferential analyses will be performed. All statistical measures (p-values and CIs) will only be of descriptive nature with no aim to draw confirmatory conclusions. If not stated otherwise, all analyses will be performed on the FAS.

No imputation for missing data is used for Other Efficacy variables, i.e. only observed data are presented, except for laboratory results reported as below the lower detection limit (or reported above a specific value) which will be imputed as described in section 5.1.

#### 5.4.3.1 Treatment response based on Responder definitions

Based on the ED from the DBPCFC at Month 12 visit, using imputation method rules used for primary analysis (depending on intercurrent event type), the following will be defined:

- Subjects defined as treatment responders:
  - If the screening ED was  $\leq 10$  mg peanut protein and the ED is  $\geq 1,000$  mg peanut protein at the post-treatment DBPCFC at Month 12
  - OR
  - If the screening ED was  $> 10$  mg peanut protein and the ED is  $\geq 2,000$  mg peanut protein at the post-treatment DBPCFC at Month 12
- Subjects defined as treatment responders:
  - If the ED is  $\geq 1,000$  mg peanut protein at the post-treatment DBPCFC at Month 12, regardless the screening ED

Based on the CRD from the DBPCFC at Month 12 visit, using imputation method rules used for primary analysis (depending on intercurrent event type), the following will be defined:

CONFIDENTIEL / Ne pas diffuser sans autorisation de DBV

CONFIDENTIAL / Do not distribute without DBV authorization

	Statistical Analysis Plan	
	EPITOPE (V712-304) – Statistical Analysis Plan	
	Référence du Document /Document Reference : CCI	Page : 45 / 74

CCI

- The percentage of subjects reaching a CRD  $\geq 1,444$  mg peanut protein at Month 12 post-treatment DBPCFC
- The percentage of subjects reaching a CRD  $\geq 3,444$  mg peanut protein at Month 12 post-treatment DBPCFC
- The percentage of subjects who passed the Month 12 post-treatment DBPCFC (no stopping criteria leading to stopping the DBPCFC at 2,000 mg)

The number and percentage of subjects will be presented by treatment group.

The analysis will be performed on the FAS and PP set. Data from these endpoints will be included in a listing.

#### 5.4.3.2 Peanut-specific IgE and IgG4 over time

Descriptive summaries of peanut-specific IgE and IgG4 over time will include actual values, absolute and relative changes from Baseline at Month 3, Month 6 and Month 12 for the overall FAS. Geometric Mean (GM) and associated Confidence Interval (CI) will also be provided.

Actual values Median ( $\pm$ IQR), GM and associated CI over time in IgE and IgG4 will be presented graphically, by treatment group, for the overall FAS.

Both parameters are known as violating the normality assumption, thus log-transformation of the data will be used.

Repeated-measures ANCOVA models (using a Compound Symmetry covariance matrix structure) will be built to compare the geometric mean absolute values in peanut-specific IgE and IgG4 using all time points evaluated up to Month 12 in the active group versus the placebo group on the FAS using observed data. Treatment group, treatment-by-time point interaction and Baseline value will be included in the model.

The SAS® code used is listed in Appendix 8.2.

Statistics reported will include: Geometric LS means and standard error at each time point (Baseline, Month 3, 6 and 12), together with the geometric LS means ratio (DBV712 250µg/Placebo), the associated 95% confidence interval and the corresponding p-values at each time point. P-value for treatment effect all time points taken together will also be provided.

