### 3.2.3 Other Efficacy Endpoints

- The percentage of subjects reaching a cumulative reactive dose  $\geq 1,444$  mg peanut protein at the post treatment DBPCFC at Month 12 in the selected active DBV712 group (250 µg) *versus* the placebo group;
- The percentage of subjects reaching a cumulative reactive dose  $\geq 3,444$  mg peanut protein at the post-treatment DBPCFC at Month 12 in the selected active DBV712 group (250 µg) *versus* the placebo group;
- The percentage of subjects unresponsive (those showing no symptoms leading to DBPCFC stop) to the highest dose of peanut protein (2,000 mg of peanut protein) in the selected active DBV712 group (250 µg) *versus* the placebo group.
- The change from baseline in peanut-specific IgE and immunoglobulin G4 subtype (IgG4) at months 3, 6 and 12 in the selected active DBV712 group (250 µg) *versus* the placebo group;
- The change from baseline in peanut SPT average wheal diameters at months 3, 6 and 12 in the selected active DBV712 group (250 µg) *versus* the placebo group,

CONFIDENTIEL / Ne pas diffuser sans autorisation de DBV

CONFIDENTIAL / Do not distribute without DBV authorization

	Statistical Analysis Plan	
	EPITOPE (V712-304) – Statistical Analysis Plan	
	Référence du Document /Document Reference : CCI	Page : 15 / 74

CCI

- Description of the quality of life questionnaires (Food Allergy Quality of Life Questionnaire [FAQLQ]/Food Allergy Independent Measure [FAIM]) and change from baseline in FAQLQ/FAIM scores at Month 12 in the selected active DBV712 group (250 µg) *versus* the placebo group (for those countries where the translated and validated questionnaires are available and used).

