#### 5.4.3.4 Skin prick test (SPT) mean wheal diameters

Descriptive analysis of SPT mean wheal diameter over time including actual values and absolute change from Baseline at Month 3, Month 6 and Month 12 will be provided for the overall FAS.

The mean wheal diameter at Month 12 in each treatment group will be compared using an analysis of covariance (ANCOVA) model on the FAS on observed data. The model will include the treatment group, adjusted for the Baseline value as covariates.

All analyses will be performed on the FAS using observed data, with no imputation of missing data. Data will also be listed.

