### 5.7.2 IgE and IgG4 specific to peanut protein components

IgE and IgG4 specific to peanut specific components will include Ara h 1, Ara h 2, and Ara h 3. IgE and IgG4 specific to peanut specific components will be summarized descriptively as continuous data at Visit 1 (baseline), Month 3, Month 6 and Month 12. Absolute and relative change from baseline at each post-baseline visit will also be presented.

Absolute change from baseline in IgE and IgG4 peanut specific components at Month 3, Month 6 and Month 12 will be analyzed using the same approach as described for IgE and IgG4 in section 5.4.3.2.

IgE and IgG4 specific to cow’s milk, egg white, house dust mites, and grass pollen will be assessed at Visit 1 (baseline) and Month 12. These will be summarized descriptively as continuous data. Absolute and relative change from baseline at Month 12 will also be presented.

All analyses will be performed on the FAS using observed data, with no imputation of missing data.

[figure not shown]
[figure not shown]
CONFIDENTIEL / Ne pas diffuser sans autorisation de DBV

CONFIDENTIAL / Do not distribute without DBV authorization

	Statistical Analysis Plan	
	EPITOPE (V712-304) – Statistical Analysis Plan	
	Référence du Document /Document Reference : CCI [REDACTED]	Page : 62 / 74

[figure not shown]
CCI [REDACTED]

All data will be included in a listing for the FAS.

	Statistical Analysis Plan	
	EPITOPE (V712-304) – Statistical Analysis Plan	
	Référence du Document /Document Reference : CCI [REDACTED]	Page : 63 / 74

CCI [REDACTED]

	Statistical Analysis Plan	
	EPITOPE (V712-304) – Statistical Analysis Plan	
	Référence du Document /Document Reference : CCI [REDACTED]	Page : 64 / 74

CCI [REDACTED]

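### The IgE/IgG4 repeated-measures model uses Baseline as both covariate and response under compound symmetry, so its visit-level standard errors are miscalibrated and its Baseline comparison is empty

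*SAP*

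**What the plan says.** SAP 5.4.3.2 analyses log-transformed peanut-specific IgE and IgG4 on observed data in the FAS, using every time point through Month 12. On structure: "Repeated-measures ANCOVA models (using a Compound Symmetry covariance matrix structure) will be built". On fixed effects: "Treatment group, treatment-by-time point interaction and Baseline value will be included in the model". No baseline-by-time term is listed, so one slope serves all time points. The outputs include "Geometric LS means and standard error at each time point (Baseline, Month 3, 6 and 12", plus the active-to-placebo ratio, its 95% CI and a p-value at each of those time points, and one p-value over all of them.

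SAP 5.2.8 defines a single baseline, the last non-missing pre-dose value. The covariate and the Baseline response are therefore the same number.

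Three other sections bear on this:

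- SAP 3.2.3 names the endpoint as "The change from baseline in peanut-specific IgE and immunoglobulin G4 subtype (IgG4) at months 3, 6 and 12". Baseline is not among the visits.
- SAP 5.4.3.4, for the skin prick test, keeps the two roles apart: "The mean wheal diameter at Month 12 in each treatment group will be compared using an analysis of covariance (ANCOVA) model", with the baseline value as covariate.
- SAP 5.7.2 says of the Ara h components that "Absolute change from baseline in IgE and IgG4 peanut specific components at Month 3, Month 6 and Month 12 will be analyzed", and then points back to the approach of 5.4.3.2.

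On status, SAP 5.4.3 states: "All statistical measures (p-values and CIs) will only be of descriptive nature with no aim to draw confirmatory conclusions".

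**The concern.** A value regressed on itself leaves almost no residual. Here the Baseline record is one of four responses per child and the same record is the covariate, so the Baseline residual variance is far below that of the later visits. Compound symmetry allows only one variance for all four time points. The Month 3, 6 and 12 comparisons are then judged against a variance that belongs to none of them. The common slope is also pulled towards 1, because the Baseline response has slope 1 on itself.

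Two things follow. The 95% CIs and p-values at Months 3, 6 and 12, for two listed efficacy endpoints, would not have their stated coverage. The model-based Baseline ratio and p-value would describe nothing a reader could use. If 5.7.2 is taken literally, the fault carries over to Ara h 1, 2 and 3.

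**Working it through.** **Inputs.** Arm sizes of 233 and 117 are from Protocol 3.1.2. The model terms and covariance are from SAP 5.4.3.2. The SAP gives no numerical figure for this model, so there is none to reproduce. It also gives no SDs or correlations. All patterns below are assumed, on the log scale, with no treatment effect and complete data unless stated.

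**Step 1: the common slope.** Let the SD be 1 at every time point and let r_t be the correlation of visit t with Baseline. The Baseline response contributes a slope of 1, so

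b = (1 + r_3 + r_6 + r_12) / 4.

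With every r = 0.7, b = (1 + 3 × 0.7)/4 = 0.775.

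**Step 2: residual variances.** At Baseline: (1 − b)² = 0.225² = 0.0506. At each later visit: 1 − 2 × 0.775 × 0.7 + 0.775² = 0.5156.

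**Step 3: what compound symmetry uses.** The single variance is close to the average of the four: (0.0506 + 3 × 0.5156)/4 = 0.3994. With 1/233 + 1/117 = 0.01284:

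- model SE = √(0.3994 × 0.01284) = 0.0716
- true SD of the later contrasts = √(0.5156 × 0.01284) = 0.0814
- ratio = 0.88

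A nominal 5% test then uses an effective critical value of 1.96 × 0.88 ≈ 1.72, which a standard normal exceeds in absolute value about 8.4% of the time.

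**Step 4: simulation.** A REML compound-symmetry fit was run on 20,000 trials per pattern, with Baseline in the response and with Months 3, 6 and 12 only. The closed-form fit used in a separate replication agreed with a standard mixed-model routine on a test dataset. Results at Month 12:

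| Assumed pattern | SE / true SD, Baseline in | SE / true SD, Baseline out | Rejects at 5%, Baseline in | Rejects at 5%, Baseline out |
|---|---|---|---|---|
| Constant correlation 0.7 | 0.879 | 0.999 | 8.4% | 4.8–5.0% |
| Constant correlation 0.8 | 0.879 | 1.005 | 8.4% | 4.8–5.0% |
| Correlation decays 0.85 per 3 months | 0.716 | 0.827 | 15.8% | 10.5% |
| SD rises 1 to 1.4 | 0.769 | 0.882 | 13.2% | 8.3% |
| Decay and rising SD | 0.655 | 0.756 | 19.8% | 14.0% |
| SD 1, 1.3, 1.1, 0.8 | 1.116 | 1.318 | 2.9% | – |
| SD 1, 1, 1, 0.8 | 1.008 | 1.165 | 4.6% | – |

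In the first two rows compound symmetry is true, so the double use of Baseline is the only cause. In the next three, the Baseline-out columns show how much is compound-symmetry misfit alone. A separate ANCOVA at Month 12, which with complete data equals the unstructured model at that visit, gives SE ratios of 0.996–1.006 and rejects 4.8–5.0% in all seven patterns.

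**Step 5: the other visits.** The replication covered all three post-baseline visits, again with Baseline in the response:

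- Constant correlation 0.5 to 0.9: SE ratio 0.87–0.90 and rejection 7.8–9.0% at Months 3, 6 and 12.
- Correlation decaying 0.5 to 0.9 per 6 months: at Month 3 the SE is too large (ratio 1.11–1.26, rejects 1.4–3.1%); at Month 6 it is too small (0.90–0.92, 7.1–7.9%); at Month 12 more so (0.68–0.76, 13.6–18.1%).

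**Step 6: the Baseline comparison.** The model-based Baseline log ratio equals (1 − b) times the observed chance imbalance, here 1 − 0.775 = 22.5% of it. In the replication its model SE was 2.0 to 10.7 times its true SD, and p fell below 0.05 in at most 0.01% of trials.

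**Step 7: the overall p-value.** Let d_0 be the Baseline difference, d_post the mean post-baseline difference and b_3 the slope from post-baseline visits only. The four-time-point effect is (d_0 + 3 d_post)/4 − [(1 + 3 b_3)/4] d_0 = (3/4)(d_post − b_3 d_0). Estimate and SE both shrink by 3/4, so z is unchanged with complete data. The simulation agrees (largest difference 7e-15). With drop-out reaching 15%, the maximum assumed in the protocol's sample-size section, and a log ratio of 0.30, mean z was 4.74 against 4.57, 4.66 against 4.51, and 3.82 against 3.68, about 4% larger with Baseline in.

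**The case against.** The SAS code in Appendix 8.2 is redacted, and it would settle which rows are responses. The reference in 5.7.2 to change at Months 3, 6 and 12 suggests a post-baseline model, since change at Baseline is always zero. This is possible. But a post-baseline model cannot produce the Baseline LS means, ratio and p-value that 5.4.3.2 promises, so the text needs correcting either way.

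Much of the larger error comes from compound symmetry rather than from double use: 10.5% of the 15.8% under decay, 14.0% of the 19.8% with rising SD as well. In two of the seven patterns, removing Baseline while keeping compound symmetry moves the Month 12 SE further from the truth. Both points stand. They are reasons to change the covariance along with the response rows, not reasons to leave the model alone.

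The percentages rest on assumed variances and complete normal data on the log scale, and ignore the rule in SAP 5.1 that sets values beyond assay limits to the limit. That stands too: the figures show a range, not a forecast. A null-effect error rate may seem of little relevance to IgG4, which Protocol 3.4 says has risen consistently in treated subjects. But the same SE sets the CI width. A test that rejects 8.4% under the null corresponds to an interval covering about 91.6% instead of 95%, whatever the true effect.

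The strongest point is that nothing turns on this. The statistics are declared descriptive, lie outside the hierarchy in SAP Table 1, and do not feed the median-based futility rule in Protocol 8.9.2. That limits the weight of the point. It does not make a mislabelled 95% interval acceptable.

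**Conclusion.** The concern holds on the SAP text. Baseline is both covariate and response, and compound symmetry spreads its near-zero residual variance over the later visits. When compound symmetry is exactly right, the double use alone makes the Month 12 SE about 12% too small and turns a 5% test into 8.4%. Under decaying correlation or rising variance the Month 12 rejection rate is 13% to 20%, partly from compound-symmetry misfit. The SE can instead be too large, at Month 3 under decay or when the SD falls late. Size and direction depend on variances and correlations that the documents do not give.

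The Baseline ratio and p-value are uninformative. The overall treatment p-value is unaffected with complete data and nearly so with drop-out. Primary, secondary and futility results are untouched. This should be corrected, but no trial decision depends on it.

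**What to change.** In SAP 5.4.3.2 and the matching code:

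- Use only Months 3, 6 and 12 as responses.
- Fit treatment, visit, treatment-by-visit, baseline and baseline-by-visit, with an unstructured covariance. Dropping Baseline alone is not enough if compound symmetry stays.
- Delete the model-based Baseline LS mean, ratio, CI and p-value, and keep the descriptive baseline summary.
- Define the overall treatment test as the average over the three post-baseline visits. This leaves the p-value essentially as it is and makes its meaning clear.
- State in 5.7.2 that the Ara h components use the same post-baseline-only model.

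The cost is a change to the model statement and a few lines of SAP text. No new data are needed, and about 350 subjects with three visits readily support an unstructured matrix.

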#### 5.4.3.3 Ratio between peanut-specific IgG4 and peanut-specific IgE

The log transformation of the ratio between peanut-specific IgG4 and peanut-specific IgE, calculated as:

$$\text{Ratio} = \log \left( \frac{\text{Peanut specific IgG4}(\text{mg/L}) \times 1000}{\text{Peanut specific IgE}(\text{kU/L}) \times 2.4} \right)$$

will be tabulated for the FAS at each time point:

- by treatment group and overall;
- for treatment responders vs. non responders (primary endpoint), by treatment group and overall.

CONFIDENTIEL / Ne pas diffuser sans autorisation de DBV

CONFIDENTIAL / Do not distribute without DBV authorization

	Statistical Analysis Plan	
	EPITOPÉ (V712-304) – Statistical Analysis Plan	
	Référence du Document /Document Reference : CCI	Page : 46 / 74

CCI

#### 5.4.3.4 Skin prick test (SPT) mean wheal diameters

Descriptive analysis of SPT mean wheal diameter over time including actual values and absolute change from Baseline at Month 3, Month 6 and Month 12 will be provided for the overall FAS.

The mean wheal diameter at Month 12 in each treatment group will be compared using an analysis of covariance (ANCOVA) model on the FAS on observed data. The model will include the treatment group, adjusted for the Baseline value as covariates.

All analyses will be performed on the FAS using observed data, with no imputation of missing data. Data will also be listed.

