**Part B**

The sample size for the efficacy part of the study is calculated based on the following assumptions:

- A 2:1 ratio in favor of the DBV712 dose *versus* placebo;
- A 40% response rate for DBV712 (optimal active dose) and a 10% response rate for placebo using missing=failure imputation method (based on a maximum drop-out rate of 15%). This will give a 30% absolute difference for the primary endpoint between active and placebo at 12 months of treatment;
- A lower bound of the 95% confidence interval (CI) of the difference between the selected active treatment and placebo response rates  $\geq 15\%$ ;
- Newcombe method is used for the computation of the CI.

Hence, the minimum number of subjects needed to ensure a power of at least 90% is 350 (approximately 233 subjects in total in the selected active DBV712 group [250 µg] and 117 subjects in the placebo group).

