### 8.5.4 Other Efficacy Analyses

The percentage of subjects reaching a cumulative dose  $\geq 1,444$  mg peanut protein at Month 12, the percentage of subjects reaching a cumulative dose  $\geq 3,444$  mg peanut protein at Month 12, and the percentage of subjects unresponsive (i.e, showing no symptoms leading to stop the DBPCFC) to the highest dose (2,000 mg peanut protein) at Month 12 will be summarized descriptively by treatment group for the ITT population using missing=failure imputation method, as well as for the PP population.

No further adjustments will be made for the other efficacy endpoints for which p-values will be provided for descriptive purpose only. The following efficacy analyses will be performed using observed data (no imputation will be done).

- Peanut-specific IgE and IgG4 analysis over time: peanut-specific IgE and IgG4 levels at baseline and changes from baseline to Months 3, 6 and 12 will be summarized descriptively by treatment group on the ITT population, using observed data.

The mean change from Baseline of the peanut-specific IgE and IgG4 will be compared.

- Skin Prick Test analysis: The mean change from baseline at Months 3, 6 and 12 in mean wheal diameter will be evaluated for each treatment group on the ITT population using observed data.
- A quality of life score from the FAQLQ/FAIM Parent Form will be summarized at Month 12 and compared to baseline for both treatment groups for the overall ITT population, using observed data. FAQLQ-Parental Form (FAQLQ-PF) questionnaires will also be summarized by main domains of quality of life using specific scores:
  - Emotional impact,
  - Food-related anxiety,
  - Social and Dietary limitations.

The relationship between FAQLQ-PF scores and treatment response will also be studied.

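### SAP 5.4.3.4 models the skin prick test difference from placebo only at Month 12, while the endpoint names Months 3, 6 and 12 (minor; non-confirmatory endpoint)

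*SAP*

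**What the plan says.** SAP 3.2.3 names the endpoint as "The change from baseline in peanut SPT average wheal diameters at months 3, 6 and 12 in the selected active DBV712 group", against placebo. Protocol 3.3.1.3 does the same. The opening of SAP 5.4.3 says of the other efficacy endpoints: "For all endpoints, descriptive statistics and inferential analyses will be performed". It adds that their p-values and intervals are descriptive and carry no confirmatory aim.

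SAP 5.4.3.4 then plans two things for SPT:

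- by-visit description: "Descriptive analysis of SPT mean wheal diameter over time including actual values and absolute change from Baseline at Month 3, Month 6 and Month 12";
- one model: "The mean wheal diameter at Month 12 in each treatment group will be compared using an analysis of covariance (ANCOVA) model on the FAS", with treatment and baseline wheal as terms, on observed values without imputation.

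Peanut-specific IgE and IgG4 come from the same visits. SAP 5.4.3.2 fits them with a repeated-measures model "using all time points evaluated up to Month 12 in the active group versus the placebo group on the FAS using observed data", and reports the arm ratio, confidence interval and p-value at each visit. SAP 5.11, which lists changes from the protocol, does not mention SPT.

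**The concern.** The endpoint has three time points, and the plan estimates an arm difference at one of them. A reader who wants the size of the SPT effect at Month 3 or Month 6, with its uncertainty, will find by-arm summaries only.

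The second issue is who enters the Month 12 estimate. An ANCOVA on children observed at Month 12 is unbiased only if missingness is unrelated to the Month 12 wheal, given arm and baseline. A likelihood model over all post-baseline visits also allows missingness to depend on the wheals seen at Months 3 and 6, which is a weaker assumption. If active-arm children whose wheals are not shrinking leave more often, the Month 12 ANCOVA makes the treatment look better than it is.

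**Working it through.** **1. Inputs from the documents.** Part B has 350 children, 233 active and 117 placebo. The dropout allowance in the sample size section is "based on a maximum drop-out rate of 15" per cent. The Month 12 analysis window in SAP 5.2.7, Table 2, is Day 365 with 21 days before and 90 days after, so 365 - 21 = 344 to 365 + 90 = 455.

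**2. The plan's own figure.** No sample size or power is stated for SPT. The 350 is for the primary endpoint, and it reproduces: with 40% against 10% responders at 233 and 117, the exact probability that the Newcombe 95% lower limit reaches 15% is 90.8%, against the stated minimum of 90%.

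**3. Children outside the comparison at the maximum allowance.** 350 × 0.15 = 52.5, so about 53 children: 233 × 0.15 ≈ 35 active and 117 × 0.15 ≈ 18 placebo. About 297 remain. The 15% was set for the food-challenge endpoint and is borrowed here as an upper guide; the documents give no SPT missingness rate.

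**4. Method.** The documents give no SPT effect, SD or correlations, so everything below is assumed. Two estimates of the Month 12 difference were compared by simulation:

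- the planned ANCOVA on children with a Month 12 wheal;
- an all-visit estimate, τ12 = c_arm + c_3·τ3 + c_6·τ6. Here c_arm, c_3 and c_6 come from regressing the Month 12 wheal on arm, baseline, Month 3 and Month 6 in observed children. τ3 and τ6 are the baseline-adjusted arm differences in all children. With monotone dropout this is equivalent to a likelihood repeated-measures fit with unstructured covariance (and a baseline slope free to differ by visit).

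**5. Results with all 15% of dropout after Month 6.** Assumptions: SD 4 mm; effects -0.5, -1 and -2 mm at Months 3, 6 and 12; post-baseline correlation 0.5 to 0.7; placebo dropout random.

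| Active-arm dropout odds per SD of Month 6 wheal change | Overstatement, Month 12 ANCOVA | Bias, all-visit estimate |
|---|---|---|
| unrelated | about 0% | within 0.5% |
| 1.6-fold (slope 0.5) | 4.4-5.6% | within 0.5% |
| 2.7-fold (slope 1.0) | 8.0-10.2% | within 0.5% |

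The all-visit standard error is 0.97 to 0.99 of the ANCOVA's, a gain of 1-3%.

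**6. Second set-up, in SD units.** True Month 12 effect -0.40 SD, correlation 0.5 or 0.7, dropout 10% or 15% after Month 6. With random dropout both methods are unbiased, and the ANCOVA variance is 1.017 to 1.037 times the all-visit variance. With active-arm dropout rising with Month 6 wheal, the ANCOVA averages -0.421 to -0.435. That is 0.021/0.40 ≈ 5% to 0.035/0.40 ≈ 9% too large. The all-visit estimate averages -0.398 to -0.401.

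**7. Less favourable dropout patterns, on the 2 mm set-up.**

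- All dropout after Month 6: bias 0.10-0.20 mm against a standard error of 0.39-0.45 mm, so about half a standard error at most.
- Dropout spread evenly before Month 3, Months 3-6 and after Month 6: about 0.03-0.13 mm (2-7%).
- 60% of dropout before Month 3: about 0.04-0.10 mm (2-5%).
- The same dependence on wheal in both arms: about 0 (within 0.03 mm).

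**The case against.** The strongest reply is that the SAP follows the protocol and goes further. Protocol 8.5.4 says the mean changes in IgE and IgG4 are to be compared, whereas for SPT "The mean change from baseline at Months 3, 6 and 12 in mean wheal diameter will be evaluated for each treatment group". On that wording a by-visit description would do, and the Month 12 ANCOVA is an addition. This explains why SPT and IgE/IgG4 differ, so one cannot say the documents give no hint of a distinction. It does not settle the matter: both documents state the endpoint against placebo, and the SAP itself chose to compare, at one visit of three.

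Some stronger readings are tempting, and the documents do not support them:

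- *The Month 3 and 6 wheals are thrown away.* They are tabulated under 5.4.3.4, by arm under the default layout in SAP 5.1. Only the modelled difference is missing.
- *The SAP breaks a promise of inference at every visit.* The sentence in 5.4.3 speaks of endpoints, not visits; a Month 12 model satisfies it.
- *Every withdrawn child is excluded.* Protocol 7.2.12 includes an SPT at early termination, and SAP 5.2.7 assigns such records by study day. One falling between Day 344 and Day 455 can enter the ANCOVA.
- *The SPT result will be biased by 10%.* That needs strong, active-arm-only dependence on wheal with all dropout after Month 6. No passage suggests it.

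It is also fair to say that the remedy is not a copy of 5.4.3.2, which uses compound symmetry. Nor does it recover anything from children who leave before any post-baseline SPT.

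**Conclusion.** The point holds as a minor one. The endpoint names three visits, and 5.4.3.4 gives a modelled arm difference at Month 12 alone, in children with an SPT in that window. With dropout unrelated to wheal, the cost is 1-3% of the standard error and no bias. With active-arm dropout after Month 6 driven by wheal, the Month 12 effect could be overstated by roughly 4-10%. It would be less with earlier dropout, and about zero if the dependence is the same in both arms.

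These percentages rest on assumed SDs, effects, correlations and dropout mechanisms. Under the 2 mm assumption the effect is more than four standard errors from zero (2/0.45 ≈ 4.4), so a shift of this size would not change how SPT is read. SPT lies outside the testing hierarchy in SAP 5.2.2, and no formal conclusion depends on it. The surer gain from a change is the two missing estimates; protection against selective dropout is secondary.

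**What to change.** In SAP 5.4.3.4, replace the Month 12 ANCOVA with a likelihood repeated-measures model:

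- outcomes: mean wheal diameter at Months 3, 6 and 12 (post-baseline rows only);
- terms: treatment, visit, treatment-by-visit and baseline wheal;
- covariance: unstructured;
- report: LS mean difference (DBV712 250 µg minus placebo) with 95% CI at each visit, labelled descriptive.

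Every randomised child with a baseline and at least one post-baseline SPT in a Month 3, 6 or 12 window then contributes, and the Month 12 estimate is kept. The cost is minor reprogramming and a few extra covariance parameters, which is negligible at about 350 children. No new data, visits or patients are needed. Children with no post-baseline SPT still do not contribute; report their number by arm beside the estimates.
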